## 5.7 Women of Childbearing Potential

Women of childbearing potential (defined as women with regular menses, women with

amenorrhea, women with irregular cycles, women using a contraceptive method that precludes withdrawal bleeding, and women who have had a tubal ligation) are required to have a negative pregnancy test within 14 days prior to the first doses of tosedostat and capecitabine.

Female and male patients (along with their female partners) are required to use two forms of acceptable contraception, including one barrier method, during participation in the study and for 3 months following the last dose of either study drug.

If a patient is suspected to be pregnant, study treatment should be immediately discontinued. In addition a positive urine test must be confirmed by a serum pregnancy test. If it is confirmed that the patient is not pregnant, the patient may resume dosing.

If a female patient or female partner of a male patient becomes pregnant during therapy or within 3 months after the last dose of either study drug, the investigator must be notified in order to facilitate outcome follow-up.

## **5.8 Duration of Therapy**

If at any time the constraints of this protocol are considered to be detrimental to the patient's health and/or the patient no longer wishes to continue protocol therapy, the protocol therapy should be discontinued and the reason(s) for discontinuation documented in the case report forms.

In the absence of treatment delays due to adverse events, treatment may continue until one of the following criteria applies:

- Documented and confirmed disease progression
- Death
- Adverse event(s) that, in the judgment of the investigator, may cause severe or permanent harm or which rule out continuation of study drug
- General or specific changes in the patient's condition render the patient unacceptable for further treatment in the judgment of the investigator
- Suspected pregnancy
- Serious non-compliance with the study protocol
- Lost to follow-up
- Patient withdraws consent
- Investigator removes the patient from study
- The Siteman Cancer Center decides to close the study

Patients who prematurely discontinue treatment for any reason will be followed as indicated in the study calendar.

## **5.9 Duration of Follow-up**

Patients will be followed every 3 months for 1 year or until death, whichever occurs first.

Patients removed from study for unacceptable adverse events will be followed until resolution or stabilization of the adverse event.

## 6.0 DOSE DELAYS/DOSE MODIFICATIONS

### 6.1 Tosedostat Dose Reduction Table

|               |                 |
|---------------|-----------------|
| Starting Dose | 120 mg po daily |
| Dose Level -1 | 60 mg po daily  |

Patients will be monitored for toxicity and the dose of tosedostat may be adjusted. Dose reduction by one dose level will be allowed. Patients requiring more than one dose reduction will be discontinued from the study.

Recommended dose reductions for tosedostat are to decrease the current dose by 60 mg. The lowest dose available is 60 mg. Doses may be held as needed for toxicity resolution during a cycle. Doses omitted for toxicity are not replaced or restored within the same cycle (meaning that the cycle remains 21 days regardless of the number of doses of taken). If a patient experiences toxicity which has not resolved to grade 2 or lower within two weeks, treatment with tosedostat should be permanently discontinued.

#### 6.1.1 Cardiac Toxicity

| Ejection Fraction Grade | Occurrence                 | Tosedostat                                                                                                                                                                                                                                                                                           |
|-------------------------|----------------------------|------------------------------------------------------------------------------------------------------------------------------------------------------------------------------------------------------------------------------------------------------------------------------------------------------|
| Grade 2*                | 1st                        | Hold Tosedostat and repeat ECHO. 
 
Hold drug until LVEF is less than or equal to 9% points of baseline and resume at the current dose.
 
If LVEF is below institutional normal limit, please hold the study drug
 
                              |
|                         | 2 nd            | Hold Tosedostat and repeat ECHO. 
 
Hold drug until LVEF is less than or equal to 9% points of baseline and resume at the next lower dose.
 
If LVEF is below institutional normal limit, please hold the study drug
 
                           |
|                         | 3 rd and beyond | Hold Tosedostat and repeat ECHO. 
 
If LVEF is above institutional normal limits: Hold drug until LVEF is less than or equal to 9% points of baseline and resume at the same dose.
 
If LVEF is below institutional normal limits: Discontinue
 
 |
| Grade 3                 | Any                        | Discontinue                                                                                                                                                                                                                                                                                          |

\*Per the PI's discretion, patients may be referred to Cardiology for a second opinion.

### 6.1.2 Hematologic Toxicity

ANC must be  $\geq 1,000$  cells/ $\mu$ l and platelet count must be  $\geq 75,000$  cells/ $\mu$ l at the start of each cycle.

| Grade                      | Occurrence      | Tosedostat                                                        |
|----------------------------|-----------------|-------------------------------------------------------------------|
| Neutrophils         |                 |                                                                   |
| Grade $\leq 2$             | Any             | Current dose                                                      |
| Grade 3                    | Any             | Hold till ANC $\geq 1,000$ , resume the current dose              |
| Grade 4                    | 1 st | Hold till ANC $\geq 1,000$ , resume the next lower dose           |
| Grade 4                    | 2 nd | Discontinue                                                       |
| Platelets           |                 |                                                                   |
| Grade $\leq 1$             | Any             | Current dose                                                      |
| Grade 2                    | Any             | Hold till platelets $\geq 75,000$ , resume the current dose level |
| Grade 3                    | Any             | Hold till platelets $\geq 75,000$ , resume the next lower dose    |
| Grade 4                    | 1 st | Hold till platelets $\geq 75,000$ , resume the next lower dose    |
|                            | 2 nd | Discontinue                                                       |
| Febrile neutropenia |                 |                                                                   |
| Grade 3                    | 1 st | Hold till ANC $\geq 1,000$ , resume the next lower dose           |
|                            | 2 nd | Discontinue                                                       |

The patient will be taken off the trial if more dose reductions are called for than are allowed.

### 6.1.3 Other Nonhematologic Toxicities Reasonably Related to Treatment

| Grade    | Occurrence      | Tosedostat                                                    |
|----------|-----------------|---------------------------------------------------------------|
| Grade 1  | Any             | Current dose                                                  |
| Grade 2* | 1 st | Hold until $\leq$ grade 1, then resume at the current dose    |
|          | 2 nd | Hold until $\leq$ grade 1, then resume at the next lower dose |
|          | 3 rd | Discontinue                                                   |
| Grade 3* | 1 st | Hold until $\leq$ grade 1, then resume the next lower dose    |
|          | 2 nd | Hold until $\leq$ grade 1, then resume the next lower dose    |
|          | 3 rd | Discontinue                                                   |
| Grade 4* | 1 st | Hold until $\leq$ grade 1, then resume the next lower dose    |

|  |                 |             |
|--|-----------------|-------------|
|  | 2 nd | Discontinue |
|--|-----------------|-------------|

\*Based off occurrence of the same repeating toxicity

Patients will be taken off the study if their treatment has to be held for more than 4 weeks for any reason.

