## 6.2 Capecitabine Dose Reduction Table

|               |                            |
|---------------|----------------------------|
| Starting Dose | 1000 mg/m  BID |
| Dose Level -1 | 750 mg/m  BID  |
| Dose Level -2 | 500 mg/m  BID  |

Reductions table is for AE's that are deemed related to capecitabine. Once dosing for capecitabine has been reduced, it should not be increased at a later time. Doses of capecitabine that are omitted for toxicity should not be replaced or restored; the patient should simply resume his/her planned treatment cycle. If capecitabine is held for longer than 2 weeks within one cycle, treatment must be permanently discontinued and the patient should come off study. Dose modifications should be based on the same AE occurrence.

| Grade   | Occurrence      | Action During Course                                                                                                              | Dose Adjustment for Next Treatment (% of starting dose) |
|---------|-----------------|-----------------------------------------------------------------------------------------------------------------------------------|---------------------------------------------------------|
| Grade 1 | Any             | Maintain dose level                                                                                                               | Maintain dose level                                     |
| Grade 2 | 1 st | Interrupt until resolved to grade 0-1                                                                                             | 100%                                                    |
|         | 2 nd |                                                                                                                                   | 75%                                                     |
|         | 3 rd |                                                                                                                                   | 50%                                                     |
|         | 4 th | Discontinue permanently                                                                                                           | --                                                      |

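### Section 6.1.3 calls for a second tosedostat reduction after two grade 3 events, but 6.1 allows only one, and patients who start at 60 mg have no stated rule

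*Combined protocol and SAP*

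**What the plan says.** **The dose ladder (6.1).** The table has a 120 mg starting dose and one lower level, 60 mg. The text below it sets three limits:
- "Dose reduction by one dose level will be allowed"
- "Patients requiring more than one dose reduction will be discontinued from the study"
- "The lowest dose available is 60 mg"

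Each reduction is a 60 mg step.

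**The non-hematologic table (6.1.3).** For grade 3, the first occurrence calls for a hold and then a step down. The second-occurrence entry is "2 nd | Hold until $\leq$ grade 1, then resume the next lower dose". Only the third says to discontinue. A footnote to the grade 2, 3 and 4 rows explains the count: "Based off occurrence of the same repeating toxicity".

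**The hematologic table (6.1.2).** The grade 3 platelet row, for any occurrence, is "Hold till platelets $\geq 75,000$ , resume the next lower dose". A closing line under that table adds: "The patient will be taken off the trial if more dose reductions are called for than are allowed". No such line follows the 6.1.3 table.

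**Capecitabine (6.2).** This drug has two lower levels, the second being "Dose Level -2 | 500 mg/m 2 BID".

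**Starting dose (5.5.3).** If two or more of six patients have a dose-limiting toxicity at Level 0, six more are treated at the next level down. If at most one of those six has one, phase II proceeds at Level -1, which is 60 mg.

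**The concern.** The grade 3 sequence of reduce, reduce, discontinue needs two doses below the starting dose, and tosedostat has one. At a second grade 3 event in a patient already reduced, the table tells the clinician to resume treatment at a dose that does not exist. The row below it suggests that the patient could still be on drug at a third event. Section 6.1 says that the same patient is out. The two instructions disagree about a severe toxicity that recurs at the lowest dose of the investigational agent. One clinician may stop and another may hold and improvise.

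The position is less settled for a patient whose first dose is 60 mg. The 6.1 ladder names only 120 mg as a starting dose, and its limit is on the number of reductions. For this patient the obstacle is the dose floor, not the number of reductions.

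**Working it through.** No rates or power figures are involved. The check applies the tables to the dose ladder.

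**Inputs.** From 6.1: start 120 mg, step 60 mg, lowest dose 60 mg, reductions allowed 1. From 5.5.3: a start at 60 mg is possible. No text provides for raising tosedostat again after a reduction, so none is assumed.

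**Step 1. The plan's own ladder.** 120 − 60 = 60 mg. One permitted reduction reaches the stated floor, so 6.1 is consistent within itself.

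**Step 2. Two grade 3 events of the same toxicity, starting at 120 mg.**

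| Event | Entry in 6.1.3 | Resulting dose | Reductions used (limit 1) |
|---|---|---|---|
| First grade 3 | step down | 120 − 60 = 60 mg | 1 |
| Second grade 3 | step down | 60 − 60 = 0 mg, not a level | 2 |

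The second entry exceeds the limit by one and calls for a dose below the floor.

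**Step 3. Same toxicity, grade 2 first and then grade 3, starting at 120 mg.** The footnote does not say whether occurrences are counted per toxicity or per toxicity and grade.
- *Per toxicity.* The first event (grade 2) resumes at the current dose, 120 mg. The return at grade 3 is the second occurrence and steps down to 60 mg. That is the first reduction, so the entry works. A third event at grade 3 reaches the third-occurrence row.
- *Per toxicity and grade.* A second grade 3 occurrence always follows a grade 3 first occurrence, which already used the reduction. The second entry then never works and the third row is never reached.

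**Step 4. Starting at 60 mg.** Entries that call for a step down:
- 6.1.1: grade 2 ejection fraction, second occurrence (1 entry).
- 6.1.2: neutrophils grade 4 first, platelets grade 3 any, platelets grade 4 first, febrile neutropenia first (4 entries).
- 6.1.3: grade 2 second, grade 3 first, grade 3 second, grade 4 first (4 entries).

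Total 1 + 4 + 4 = 9. Each would give 60 − 60 = 0 mg, so none of the nine can be carried out.

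The removal rules in 6.1 and 6.1.2 apply when more reductions are needed than are allowed. At the first such event, one is called for and one is allowed. Since 1 does not exceed 1, neither rule is clearly triggered.

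**Step 5. Comparison with capecitabine.** The grade 3 rows in 6.2 have the same three steps: 75% × 1000 = 750 mg/m², 50% × 1000 = 500 mg/m², then stop. Both reduced doses are listed levels, so the sequence works there.

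**The case against.** The best answer is that the plan already resolves the conflict. Section 6.1 is the parent of all three tables and discontinues anyone who needs a second reduction. The line closing 6.1.2 says much the same, is not worded as limited to blood counts, and stands directly before 6.1.3. It settles the matching gap when grade 3 thrombocytopenia recurs. For a 120 mg starter this stands: a reader who returns to 6.1 will stop treatment. What remains is a table entry that contradicts its parent rule on the grade 3 then grade 3 path. The answer does not clearly reach a 60 mg starter.

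A reader might infer that the second-occurrence row can never be followed, that the third row is always out of reach, and that the entry should simply read as a discontinuation. The documents do not support this. The footnote leaves the counting open, and under per-toxicity counting a grade 2 event followed by a grade 3 event uses the row validly. A flat discontinuation would then deny that patient the one reduction that 6.1 allows.

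A reader might also take the table as permission to treat again at 60 mg after a second grade 3 event. It gives none: it calls for a lower dose, and there is no lower dose.

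**Conclusion.** The point holds, and it is minor. Two things are established:

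1. For a patient already reduced from 120 to 60 mg at a first grade 3 event, the second-occurrence entry in 6.1.3 cannot be carried out and conflicts with 6.1. This holds under either way of counting occurrences.
2. For a patient who starts at 60 mg, none of the nine step-down entries in 6.1.1 to 6.1.3 can be carried out, and the one-reduction limit does not clearly say what to do. This gap is conditional on Level -1 being used.

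The first conclusion rests on there being no re-escalation of tosedostat, since no text provides for it. Practical harm is limited because 6.1 already discontinues 120 mg starters who need a second reduction. The documents give no basis for a number of affected patients or for an effect on progression-free survival.

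**What to change.** 1. Add to 6.1, stated to apply to 6.1.1 through 6.1.3: *If a tosedostat reduction is called for and the patient has already had one reduction or is already at 60 mg, discontinue the patient from study treatment.* The first condition also covers an earlier reduction for a different toxicity. The second covers patients who start at 60 mg.
2. State in the 6.1.3 footnote whether occurrences are counted per toxicity or per toxicity and grade.
3. Reword the grade 3 second-occurrence entry to: *If at 120 mg with no prior reduction, hold until grade 1 or lower and resume at 60 mg; otherwise discontinue.* If counting is per toxicity and grade, the entry becomes simply *Discontinue* and the third-occurrence row is deleted.
4. State whether *Discontinue* in the tables means stopping tosedostat only or coming off study. The table entries sit in a column headed for tosedostat, while the limit in 6.1 removes the patient from the study. The sentence added in item 1 should use the same meaning.

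The cost is a few lines in an amendment. No new visits, data or patients are needed.

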## 6.2 Capecitabine Dose Reduction Table

|               |                            |
|---------------|----------------------------|
| Starting Dose | 1000 mg/m  BID |
| Dose Level -1 | 750 mg/m  BID  |
| Dose Level -2 | 500 mg/m  BID  |

Reductions table is for AE's that are deemed related to capecitabine. Once dosing for capecitabine has been reduced, it should not be increased at a later time. Doses of capecitabine that are omitted for toxicity should not be replaced or restored; the patient should simply resume his/her planned treatment cycle. If capecitabine is held for longer than 2 weeks within one cycle, treatment must be permanently discontinued and the patient should come off study. Dose modifications should be based on the same AE occurrence.

| Grade   | Occurrence      | Action During Course                                                                                                              | Dose Adjustment for Next Treatment (% of starting dose) |
|---------|-----------------|-----------------------------------------------------------------------------------------------------------------------------------|---------------------------------------------------------|
| Grade 1 | Any             | Maintain dose level                                                                                                               | Maintain dose level                                     |
| Grade 2 | 1 st | Interrupt until resolved to grade 0-1                                                                                             | 100%                                                    |
|         | 2 nd |                                                                                                                                   | 75%                                                     |
|         | 3 rd |                                                                                                                                   | 50%                                                     |
|         | 4 th | Discontinue permanently                                                                                                           | --                                                      |
| Grade 3 | 1 st | Interrupt until resolved to grade 0-1                                                                                             | 75%                                                     |
|         | 2 nd |                                                                                                                                   | 50%                                                     |
|         | 3 rd | Discontinue permanently                                                                                                           | --                                                      |
| Grade 4 | 1 st | Discontinue permanently OR if MD deems it to be in the patient's best interest to continue, interrupt until resolved to grade 0-1 | 50%                                                     |

For grade 3 or 4 thromboembolic events which are related to capecitabine, hold capecitabine, start anticoagulation therapy Lovenox (preferred choice), and resume at the investigator's discretion.

Capecitabine or Tosedostat can be continued while the other drug is being held (if no hold criteria are met for the other drug).

### 6.3 Stopping Rule for Excess Toxicity

In the event of any deaths on study thought to be possibly, probably, or definitely related to study treatment, the study will be suspended, AEs will be assessed, and the study will be considered for revision or closure.

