### 5.5.3 Dose De-Escalation Criteria

Dose de-escalations will proceed as follows after the occurrence of dose-limiting toxicity (DLT):

| Number of Patients with DLT at a Given Dose Level | De-Escalation Decision Rule                                                                                                                                                                       |
|----------------------------------------------------------|----------------------------------------------------------------------------------------------------------------------------------------------------------------------------------------------------------|
| 0 or 1 out of 6                                          | If Dose Level 0: If 0-1 patients experience a DLT move to the phase II portion at Dose Level 0.

If Dose Level -1: If 0-1 patients experience a DLT, move to the phase II portion at Dose Level -1 |
| ≥ 2 out of 6                                             | Dosing at this dose level will be stopped and 6 additional patients will be entered at the next lowest dose level, if available.                                                                         |

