### 5.5.4 Toxicity, Response, and DLT Evaluations

All patients who receive any study treatment are evaluable for toxicity. Patients are evaluated from first receiving study treatment until a 30-day follow up after the conclusion of treatment or death.

All patients are evaluable for disease response unless they come off study due to treatment related adverse events(s) prior to completion of Cycle 2 and have not had any disease assessment.

A patient is evaluable for DLT assessment only if enrolled in the phase I portion and only during Cycle 1 of treatment. If the patient is not able to be treated on Day 1 of Cycle 2, then s/he is still considered in Cycle 1 active treatment and can experience a DLT. Once the patient has been treated in Cycle 2, s/he will no longer be evaluated for DLTs in all subsequent cycles.

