### **13.0 DATA AND SAFETY MONITORING**

In compliance with the Washington University Institutional Data and Safety Monitoring Plan, the Principal Investigator will provide a Data and Safety Monitoring (DSM) report to the Washington University Quality Assurance and Safety Monitoring Committee (QASMC) semi-annually beginning six months after accrual has opened (if at least five patients have been enrolled) or one year after accrual has opened (if fewer than five patients have been enrolled at the six-month mark).

During the phase I dose escalation, the Principal Investigator will review all patient data at least monthly (or before each dose-escalation if occurring sooner than monthly), and provide a semi-annual report to the Quality Assurance and Safety Monitoring Committee (QASMC). During the phase II, the Principal Investigator will review all patient data at least every six months, and provide a semi-annual report to the QASMC. This report will include:

- HRPO protocol number, protocol title, Principal Investigator name, data coordinator name, regulatory coordinator name, and statistician
- Date of initial HRPO approval, date of most recent consent HRPO approval/revision, date of HRPO expiration, date of most recent QA audit, study status, and phase of study
- History of study including summary of substantive amendments; summary of accrual suspensions including start/stop dates and reason; and summary of protocol exceptions, error, or breach of confidentiality including start/stop dates and reason

- Study-wide target accrual and study-wide actual accrual
- Protocol activation date
- Average rate of accrual observed in year 1, year 2, and subsequent years
- Expected accrual end date and accrual by cohort
- Objectives of protocol with supporting data and list the number of participants who have met each objective
- Measures of efficacy
- Early stopping rules with supporting data and list the number of participants who have met the early stopping rules
- Summary of toxicities separated by cohorts with the number of dose-limiting toxicities indicated
- Abstract submissions/publications
- Summary of any recent literature that may affect the safety or ethics of the study

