## **14.0 STATISTICAL CONSIDERATIONS**

### **14.1 Sample Size**

In the phase I part of the study, a de-escalation 3+3 design is used to determine the recommended phase II dose of tosedostat when combined with capecitabine in patients with advanced or metastatic pancreatic adenocarcinoma. The minimal number of patients needed for the phase I part of the study is 6 patients assuming no DLT is observed in Dose Level 1. The maximal number of patients is 12 patients.

For the phase II part of the study, the primary endpoint of the study is to assess the progression-free survival (PFS) of the combination therapy. Based on historical data, the PFS of 2.0 months was observed with either 5-FU or capecitabine in the second-line setting, so a median PFS of 4 months for the combination regimen would be considered clinically meaningful for further development. With a sample size of 36 patients including 3-6 patients from the phase I portion, the study has power 0.80 to identify an increase of the median PFS (2.0 to 4.0 months) at a 0.05 significance level, assuming 12 months of accrual and 6 months of follow-up. We will consider this phase II part as a pilot study for the PFS as endpoint; therefore a sample size of 36 is adequate. We expect to enroll 3-4 patients per month; therefore it is feasible to recruit 36 patients within 1 year.

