### **14.3 Interim Analysis**

After 10 evaluable patients have enrolled to the phase II portion of the study, an interim analysis will be conducted to look at response to date to assess for continuation of the study.

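### In phase II the only study-level toxicity stopping rule is triggered by a treatment-related death, so about 30 patients are added to a dose cleared on 6 with no mandated review of excess non-fatal toxicity

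*Combined protocol and SAP*

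**What the plan says.** **Phase I.** Section 5.5.3 clears the starting level on 0 or 1 DLTs in 6: "If 0-1 patients experience a DLT move to the phase II portion at Dose Level 0". At 2 or more of 6 the level is rejected: "Dosing at this dose level will be stopped and 6 additional patients will be entered at the next lowest dose level, if available". Section 14.1 gives the resulting phase I size: "The minimal number of patients needed for the phase I part of the study is 6 patients" and "The maximal number of patients is 12 patients".

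**Phase II.** Section 5.4 continues enrolment to 36 evaluable patients, counting the phase I patients treated at the RP2D. DLT evaluation does not continue with it. Section 5.5.4 states: "A patient is evaluable for DLT assessment only if enrolled in the phase I portion and only during Cycle 1 of treatment".

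**Study-level stopping.** Section 6.3 reads: "In the event of any deaths on study thought to be possibly, probably, or definitely related to study treatment, the study will be suspended". Adverse events are then assessed, and revision or closure is considered. No other trigger is given.

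**Other oversight.**
- Section 14.3, after 10 evaluable phase II patients: "an interim analysis will be conducted to look at response to date to assess for continuation of the study".
- Section 13.0 sets at least monthly investigator review in phase I, and then: "During the phase II, the Principal Investigator will review all patient data at least every six months".
- Section 13.0 also requires semi-annual QASMC reports, continuing monitoring for serious toxicity by the investigator and coordinator, and adverse event reporting to HRPO and QASMC under institutional guidelines. The report must cover early stopping rules and toxicities by cohort with DLT numbers.
- Section 5.8 allows the cancer center to close the study, without stating a criterion.
- Sections 6.1 and 6.2 govern dose changes in individual patients.

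**The concern.** The protocol has a numerical tolerability standard, 2 DLTs in 6, and applies it only to the first cohort at each level. Once phase II opens at the same dose, nothing compares the accumulating experience with that standard. A run of non-fatal severe events would lead to individual dose changes, but no study-level review is mandated.

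The protocol itself gives reasons to expect such events. Section 1.4 limits the tosedostat dose because of reported cardiac events and describes Grade 4 thrombocytopenia with the drug. Section 5.6 refers to the thrombocytopenic effect of capecitabine.

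Two things are at stake. The first is the exposure of the phase II patients. The second is the RP2D itself, a phase I primary objective: it rests on 6 patients and is never checked against the larger group treated at it. The reporting template in section 13.0 also asks for stopping-rule and DLT information that, for non-fatal toxicity in phase II, the plan does not generate.

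**Working it through.** **Inputs from the plan.** Cohort of 6; pass on 0-1 DLTs, reject on 2 or more (5.5.3). 36 evaluable patients in total (5.4). Accrual of 3-4 per month (14.1). Reviews at least six-monthly in phase II (13.0). The true DLT rate p is not in the documents, so I use a range.

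**1. The plan's counts.** One or two levels of 6 give 6 or 12 phase I patients, as section 14.1 states. Patients added after clearance: 36 − 6 = 30. Section 14.1 speaks of 3-6 phase I patients within the 36. If only 3 counted, 33 would be added, but the 6-patient cohort points to 30.

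**2. Chance that a dose passes phase I.** P(X ≤ 1) = (1−p)^6 + 6p(1−p)^5.
- p = 0.30: 0.1176 + 0.3025 = 0.42
- p = 0.40: 0.0467 + 0.1866 = 0.23

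**3. What 6 patients can exclude.** After 1 DLT in 6, the one-sided 95% Clopper-Pearson upper bound solves P(X ≤ 1 | n = 6, p) = 0.05, giving p = 0.58. After 0 of 6 it is 0.39.

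**4. Exposure between reviews.** 6 months × 3-4 per month = 18-24 patients.

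**5. How often the death trigger would act.** With assumed related-death rates of 1%, 2% and 5%, the chance of no related death in 30 patients is 0.99^30 = 0.74, 0.98^30 = 0.55 and 0.95^30 = 0.21.

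**6. What an illustrative rule would do.** Carry the 2-in-6 fraction forward as a pause at 4 or more of 12, 6 or more of 18, or 8 or more of 24, counting the phase I cohort. Condition on phase I having passed and add binomial groups of 6. For p = 0.40:
- Given a pass, the first cohort had 0 DLTs with probability 0.0467/0.2333 = 0.20 and 1 DLT with probability 0.80.
- Pause at 12 = 0.20 × P(at least 4 of 6) + 0.80 × P(at least 3 of 6) = 0.20 × 0.179 + 0.80 × 0.456 = 0.40.
- Pause at 18 and at 24: a further 0.18 and 0.10. Total 0.68.
- Mean enrolment = 12(0.400) + 18(0.180) + 24(0.104) + 36(0.316) = 21.9.

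| True DLT rate | Passes phase I | Expected DLT-type events in next 30 | Pause, given a pass |
|---|---|---|---|
| 10% | 0.89 | 3 | 0.008 |
| 20% | 0.66 | 6 | 0.10 |
| 30% | 0.42 | 9 | 0.36 |
| one third | 0.35 | 10 | 0.47 |
| 40% | 0.23 | 12 | 0.68 |
| 50% | 0.11 | 15 | 0.90 |

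**7. Sensitivity.** The table assumes that phase II detects events as fully as phase I. If the true rate is 40% but only 30% is recorded in phase II, the pause probability falls from 0.68 to 0.38. If only 20% is recorded, it falls to 0.12. If accrual continues while a 21-day cycle completes (about 0.7 month), about 2-3 more patients enter before a pause. Mean enrolment at 40% is then about 21.9 + 0.68 × (2.1 to 2.8), or 23 to 24.

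**The case against.** The strongest reply is that toxicity in phase II is monitored. Adverse events are graded and collected. Sections 6.1 and 6.2 hold, reduce or discontinue treatment in individual patients. ECGs are weekly in Cycle 1, the investigator and coordinator watch continuously, and QASMC receives toxicity by cohort. Six months is a minimum frequency, and the center can close the study. All of this stands. A reader might infer that any number of non-fatal events would leave the trial running. The documents do not support that: a pause is possible at any time, but none is mandated.

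A reader might also infer from section 7.3, which covers only unanticipated problems acknowledged by HRPO, that an expected treatment-related death has no route to QASMC before the semi-annual report. That does not follow either. Section 13.0 sends adverse events to HRPO and QASMC under institutional guidelines that are not available here.

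Third, the dose does not rest on 6 patients alone. Section 1.4 reports a single-agent solid-tumor MTD of 240 mg against the 120 mg used here, and states that there are no significant overlapping toxicities. The binomial figures use none of this. It makes high DLT rates less likely, but it does not supply a rule for the case where they occur with the combination.

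Finally, the illustrative rule is weak near the boundary (0.36 at 30%, 0.47 at one third), and a 40% rate passes phase I less than a quarter of the time. Calendar footnote I limits weekly CBC and CMP to Cycle 1 of phase I, so several hematologic and electrolyte DLTs would be under-counted in phase II. Both limits are real. They reduce the gain from the rule without closing the gap.

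**Conclusion.** The point holds as a gap in study-level rules, not as an absence of monitoring. Phase II has one study-level toxicity trigger, a treatment-related death, and no threshold or required action for non-fatal toxicity. A dose with a true DLT rate of 30% or 40% clears phase I with probability 0.42 or 0.23, and about 30 more patients can then be treated without a mandated review. The protocol's own rejection fraction, carried forward, would be useful against clearly excessive rates (0.68 at 40%, 0.90 at 50%), modest at 30% to one third, and rarely triggered at 10%.

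The figures rest on assumed DLT rates, independent patients, the same rate in both phases, full capture of Cycle 1 events, and completed cycles at each look. Incomplete capture lowers the pause probabilities. I rate this as a change the sponsor should make. It does not show that the chosen dose is unsafe.

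**What to change.** - **Section 5.5.4:** record Cycle 1 DLT-type events, using the section 5.5.2 definitions, for every patient treated at the RP2D.
- **Section 6.3:** add a study-level pause in accrual for safety review if the cumulative proportion reaches the fraction that section 5.5.3 already treats as unacceptable, for example checked at 12, 18 and 24 patients. The exact threshold is for the sponsor to set, with its operating characteristics stated. State who conducts the review and who decides that accrual resumes. The pause changes no dose and no patient's treatment.
- **Laboratory data:** state whether phase II events will be counted from data already scheduled, accepting some under-counting and lower pause probabilities, or reconcile calendar footnote I with the new use of the DLT definitions.

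The cost is protocol wording, DLT forms for about 30 more patients (the form already exists in section 11.0), and a chance of an unnecessary pause of about 1% at a true 10% rate and 10% at 20%. If the laboratory schedule is changed, the extra sampling is a further cost.
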